8.0 Study Endpoints

8.1 Primary and secondary study endpoints:

Our primary end point, socket comfort, will be assessed using the Socket Comfort Score (Hanspal, Fisher et al. 2003) an ordinal scale where 0 = the most uncomfortable socket fit imaginable and 10 = the most comfortable socket fit. Poor socket comfort is one of the most common issues experienced by prosthesis users. Like pain, comfort is subjective and difficult to measure. Therefore, pain-measurement methods such as the numerical rating scale (NRS) were used as models for quantifying and communicating socket comfort. The Socket Comfort Score asks the standard question, “On a 0 to 10 scale, if 0 represents the most uncomfortable socket fit you can imagine, and 10 represents the most comfortable socket fit, how would you score the comfort of the socket fit of your artificial limb at the moment?”

Our secondary end point, functional performance, will be assessed using instrumented motion analysis to record biomechanics of walking at different speeds, a 5-time Rapid Sit-to-Stand Test (RSTS), Four-Square-Step Test (FSST), and T-test of Agility. The 5-time Rapid Sit-to-Stand Test, Four-

PROTOCOL TITLE: Functional Performance Evaluation of the Northwestern University Flexible Sub-Ischial Vacuum (NU-FlexSIV) Socket for Persons with Transfemoral Amputation

Square-Step Test, and T-test of Agility are standardized clinical measures of performance. We will also assess patient reported functional performance, quality of life and satisfaction with device using the Orthotic and Prosthetic Users' Survey (OPUS) (Heinemann, Bode et al. 2003).

8.2 Primary or secondary safety endpoints:

N/A

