11.0 Data and Specimen Management

11.1 Data analysis:

Before analyses begin, all variables will be plotted using histograms to inspect the shape of distributions and to check for outliers. We will not drop cases nor transform variables but if we identify any possibility that assumptions have been violated, we will employ alternative analysis approaches. As part of data screening, we will describe the amount of data that are missing, and we will compare participants with and without missing data.

Hypothesis 1: We hypothesize that the NU-FlexSIV Socket will provide increased comfort compared to the ischial containment socket.

Our primary end point is Socket Comfort Score at 6 weeks, which has been reported to have a sensitivity to socket change of 1 to 3 points (Hanspal, Fisher et al. 2003). Additionally, it has been argued that the Socket Comfort Score may be considered a continuous variable, and therefore suitable for parametric analysis, given the large number of ordered categories and the linear nature of changes in socket comfort with different configurations of socket conditions (Fatone, Dillon et al. 2015). Hence, a matched pairs t-test ($\alpha=0.05$) will be used to assess the primary outcome, Socket Comfort Score.

Hypothesis 2a: We hypothesize that the NU-FlexSIV Socket will allow greater prosthetic side hip range of motion, in particular increased hip extension, leading to increased prosthetic side step length and hence walking speed compared to the ischial containment socket.

Hypothesis 2b: We hypothesize that step width and lateral trunk flexion over the prosthetic limb will not differ between the NU-FlexSIV Socket and ischial containment socket.

For these secondary hypotheses, data analysis will include the following gait variables: walking speed (m/s), step width (m), step length (m), sagittal plane hip range of motion (degrees), maximum hip extension (degrees), and lateral trunk lean over the prosthetic limb during stance (degrees). A multiple analysis of variance (MANOVA, $\alpha=0.05$) will be used to compare gait variables across socket conditions as it is the most rigorous approach given the relationship that exists between these dependent variables (e.g., walking velocity and step length are correlated). The challenge of this approach is being convinced that underlying assumptions are met.

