Hypothesis 2c: We hypothesize that the NU-FlexSIV Socket will result in faster times to perform the 5-Times Rapid Sit-to-Stand Test, Four Square Step Test and T-Test of Agility compared to the ischial containment socket.

PROTOCOL TITLE: Functional Performance Evaluation of the Northwestern University Flexible Sub-Ischial Vacuum (NU-FlexSIV) Socket for Persons with Transfemoral Amputation

The difference in these timed performance tests across socket conditions will be tested using repeated measures t-tests with alpha=0.05 which will be adjusted using the Bonferroni correction to account for Type 1 error.

Hypothesis 3: We hypothesize that the NU-FlexSIV Socket will result in better health-related quality of life and satisfaction with device as assessed using the OPUS compared to the ischial containment socket.

The OPUS uses Likert scale responses for each item of each module. However, these responses can be converted into a single score for each module. If assumptions of normality are met, analysis with parametric procedures can be used to assess differences in module scores between sockets. Hence, we will use repeated measures t-tests with alpha=0.05 which will be adjusted using the Bonferroni correction to account for Type 1 error.

11.2 Power analysis:

To determine a sample size estimate, we have utilized data obtained from a previous pilot study.⁴⁴ In that study, we collected Socket Comfort Scores from six persons with unilateral transfemoral amputation wearing an ischial ramal containment socket and the same socket with a wider medio-lateral dimension (effect size, $d = 0.754$). Using the G*Power computer program, this effect size was used to estimate sample size. This data was used because we do not have pilot data for this particular study design. For a 2-tailed matched pairs t-test we would need a total sample size of 25 to detect an effect size of 0.754 with a critical alpha of 0.05 and power of 0.95. In order to account for possible attrition in subject numbers we will recruit 35 persons with unilateral transfemoral amputation.

11.3 Steps to be taken to secure the data to maintain confidentiality during storage, use, and transmission:

All personnel involved with the study have or will complete IRB required training.

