PROTOCOL TITLE: Functional Performance Evaluation of the Northwestern University Flexible Sub-Ischial Vacuum (NU-FlexSIV) Socket for Persons with Transfemoral Amputation

possible to tell while processing the motion analysis data what socket the subject was wearing because the data is viewed only as a stick figure (Figure 6).

- Performance and patient-reported measures can be administered fully clothed, which will disguise the socket being tested. During these assessments, subjects will be instructed not to reveal to the assessor which socket they are wearing.

Given the customized, manually-fabricated nature of prosthetic sockets, each test socket will be provided to study subjects by a separate Certified Prosthetist known for their skill with the particular socket design. This will ensure that each socket is the best and most consistent example of each particular socket design.

Since accommodation to sockets is unknown, data will be collected at baseline (within one week of definitive socket fitting) and after 3 and 6 weeks of every day socket use. These time points were chosen to enhance subject retention. Since we anticipate that one socket will be more comfortable than the other, it is possible that some subjects will find it challenging to use the less comfortable socket for a long period of time. By keeping each testing phase reasonably short (i.e., 6 weeks) we hope to retain as many subjects as possible. Additionally, by collecting data at 3 time points, we hope that if subjects are unable to continue to wear the socket for the entire six weeks, we will have initial and intermediate times points for comparison.

Step activity monitors attached to the test prostheses will allow monitoring of every day socket use. This will provide information regarding compliance with use of each prosthesis. As a secondary consideration, it will allow us to check whether there is a relationship between comfort and step activity.

When assessing the biomechanics of walking data consistency will be assured by (1) collecting all data in the same laboratory using the same instrumentation; (2) having marker placement conducted by the same experienced person who has been shown previously to have high reliability in this task; and (3) having a single person post-process all the data.

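### Holm's step-down procedure should replace single-step Bonferroni for the three timed tests and the two OPUS outcomes: same 0.05 family-wise bound, never fewer rejections

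*Combined protocol and SAP*

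**What the plan says.** Section 11.1 sets the analysis of two groups of secondary outcomes.

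- **Hypothesis 2c** predicts "faster times to perform the 5-Times Rapid Sit-to-Stand Test, Four Square Step Test and T-Test of Agility" with the NU-FlexSIV Socket. The plan states: "The difference in these timed performance tests across socket conditions will be tested using repeated measures t-tests with alpha=0.05", adjusted by Bonferroni.
- **Hypothesis 3** predicts "better health-related quality of life and satisfaction with device as assessed using the OPUS". It uses the same wording: "repeated measures t-tests with alpha=0.05 which will be adjusted using the Bonferroni correction to account for Type 1 error".

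No divisor, family definition or step-down rule is given. The hypotheses name three timed tests and two OPUS outcomes, so the natural per-test levels are 0.05/3 = 0.0167 and 0.05/2 = 0.025. Section 8.1 lists a third OPUS domain: "We will also assess patient reported functional performance, quality of life and satisfaction with device".

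Section 11.1 also says that "if we identify any possibility that assumptions have been violated, we will employ alternative analysis approaches". It fixes a visit only for the primary outcome: "Our primary end point is Socket Comfort Score at 6 weeks". The sample size in section 11.2 is set for that outcome alone.

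**The concern.** Single-step Bonferroni holds every test in a family to the strictest level, whatever the other tests show. Holm applies that level only to the smallest p-value and relaxes it after each rejection, under the same overall bound. For hypothesis testing over a fixed family, Bonferroni therefore has no advantage in the bound and can only lose rejections.

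The loss is greatest when several effects are real, and that is what the plan predicts: gains on all three timed tests and on both OPUS outcomes. These outcomes carry part of Aim 2 and all of Aim 3, and no power was planned for them. Section 11.4 defends the cross-over partly on statistical efficiency, given the cost of custom sockets; the same reasoning favours the more efficient adjustment.

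**Working it through.** **Inputs from the protocol.** Alpha 0.05, paired t-tests, families of three and two (section 11.1); 25 completers, d = 0.754 for the Socket Comfort Score, two-tailed (section 11.2). **Assumed, because the documents do not say:** two-sided secondary tests, standardised paired effects dz, and correlations r between outcomes.

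**1. The plan's own figure.** Paired-t power is P(|T| > t at 1 − α/2, n − 1 df), where T is noncentral t with noncentrality d√n. For d = 0.754 and n = 25 the noncentrality is 0.754 × 5 = 3.77 and power is 0.951; at n = 24 it is 0.942. The stated 25 for power 0.95 reproduces.

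**2. Thresholds.**

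| Ordered p-value | Bonferroni, 3 tests | Holm, 3 tests | Bonferroni, 2 tests | Holm, 2 tests |
|---|---|---|---|---|
| smallest | 0.0167 | 0.0167 | 0.025 | 0.025 |
| next | 0.0167 | 0.025 | 0.025 | 0.05 |
| last | 0.0167 | 0.05 | – | – |

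Holm stops at the first non-significant test. Its first threshold equals Bonferroni's and the later ones are larger, so its rejections always include Bonferroni's.

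**3. The error bound.** Let m of the k hypotheses be true nulls. The first true null that Holm rejects is reached after at most k − m other rejections, so its threshold is at most 0.05/m. The chance that any of the m null p-values falls at or below 0.05/m is at most m × 0.05/m = 0.05. No independence or normality is used, only valid p-values, so the argument survives a switch to other tests.

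**4. Single-test power.** At n = 25 and dz = 0.6 the noncentrality is 0.6 × 5 = 3.0. Power is 0.665 at 0.0167, 0.726 at 0.025 and 0.821 at 0.05. Bonferroni over three tests keeps each at 0.665; Holm lets some tests use the larger levels.

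**5. Simulated power, all effects real.** 100,000 trials per setting, equicorrelated normal paired differences, n = 25.

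| Setting | Bonferroni | Holm | Gain |
|---|---|---|---|
| 3 tests, dz 0.4, r 0.5, per test | 0.304 | 0.362 | 0.058 |
| 3 tests, dz 0.6, r 0.5, per test | 0.665 | 0.752 | 0.087 |
| 3 tests, dz 0.754, r 0.5, per test | 0.875 | 0.932 | 0.057 |
| 3 tests, dz 0.4/0.6/0.8, r 0.5, per test | 0.628 | 0.707 | 0.079 |
| 3 tests, dz 0.6, r 0.3, per test | 0.666 | 0.761 | 0.095 |
| 3 tests, dz 0.6, r 0.7, per test | 0.664 | 0.743 | 0.079 |
| 3 tests, dz 0.6, r 0.5, all three significant | 0.416 | 0.615 | 0.199 |
| 3 tests, dz 0.6, r 0.5, at least one significant | 0.885 | 0.885 | 0 |
| 2 tests, dz 0.6, r 0.5, per test | 0.725 | 0.784 | 0.059 |
| 2 tests, dz 0.6, r 0.5, both significant | 0.585 | 0.701 | 0.116 |

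A separate simulation at a small effect (three tests, dz 0.3, r 0.5) gave 0.163 to 0.193 per test, a gain of 0.030.

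**6. Some effects null (three tests, dz 0.6, r 0.5).**

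| Real effects | Power per real effect, Bonferroni to Holm | Family-wise error, Bonferroni to Holm |
|---|---|---|
| two of three | 0.665 to 0.702 | 0.017 to 0.036 |
| one of three | 0.664 to 0.666 | 0.031 to 0.041 |
| none | – | 0.046 under both |

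Over all settings in the separate simulation (r from 0 to 0.8), Holm's family-wise error was at most 0.0493 for three tests and 0.0496 for two. No simulated trial had a Bonferroni rejection that Holm missed over the same family.

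**7. If OPUS function joins the family.** Holm over three need not beat Bonferroni over two. At dz = 0.6, quality-of-life power goes from 0.727 to 0.753 if all three effects are real, but from 0.727 to 0.704 if function has no effect.

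**The case against.** Nothing in the plan is invalid, and Bonferroni has one real merit: it comes with matching simultaneous confidence intervals, which Holm does not provide in simple form. A Bonferroni-level interval may include zero for a test that Holm rejects. That stands as a small cost.

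The largest gains assume that every effect is real. The only effect size in the documents is for the Socket Comfort Score, from six people in a different socket comparison. The Background cites a cross-over trial of ten people in which gait and balance did not differ between a brimless and an ischial containment socket, so a null effect on, for example, the Four Square Step Test is plausible. With one null among the three, the gain is only 0.702 − 0.665 = 0.037, and the actual error about doubles, still within the bound. This limits the size of the benefit; it does not remove it.

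The figure for all three tests significant matters most if Hypothesis 2c is one joint claim. Then no adjustment is needed, and power with each test at 0.05 would be 0.640. The plan's own correction points to separate claims, so per-test power is the fairer summary.

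Finally, the Hypothesis 3 family could be read as two or three. Holm's advantage holds for either size, but only against Bonferroni over the same family.

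**Conclusion.** The concern holds, as an improvement to secondary analyses and not as an error. That Holm keeps the 0.05 bound and rejects at least what Bonferroni rejects depends on no assumption about effects or correlations. The size of the gain does. At n = 25 with all effects real and dz from 0.4 to 0.754, it is about 0.06 to 0.10 in per-test power for the three timed tests; for two OPUS outcomes at dz = 0.6 it is about 0.06. It shrinks to about 0.04 with two real effects of three and vanishes with one.

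Both methods hold 0.05 within each family, not across hypotheses: two independent families at 0.05 give 1 − 0.95² = 0.0975. The change to Holm leaves that as it is. The primary analysis and the 25 completers are untouched.

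**What to change.** In section 11.1, before any outcome data are seen, replace the Bonferroni sentences.

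Under Hypothesis 2c:

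> The three timed tests at 6 weeks form one family, tested at a family-wise 0.05 with the Holm step-down procedure (smallest p against 0.0167, next 0.025, last 0.05, stopping at the first non-significant test).

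Under Hypothesis 3:

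> OPUS quality of life and satisfaction with device at 6 weeks form one family of two, tested at a family-wise 0.05 with the Holm step-down procedure (0.025, then 0.05).

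Report Bonferroni-level confidence intervals beside the Holm p-values, and say that the two may occasionally disagree.

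The 6-week visit is carried over from the primary endpoint; the plan names no visit for these outcomes, so the investigators should confirm it. Two related details can be settled in the same edit, although the case for Holm does not depend on them:

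- whether OPUS function is tested, in which case the family is three (0.0167, 0.025, 0.05);
- how earlier visits enter for subjects without a 6-week visit, since section 11.4 says only that "we will have initial and intermediate times points for comparison". The rule should match the one for the primary endpoint.

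The cost is one sentence per hypothesis and these short decisions, with no new subjects, visits or data.

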The standard-of-care IC socket design will be determined on a per-subject basis by the Certified Prosthetist using standard clinical practice procedures. However, subject selection criteria will serve to decrease the variability in patient presentation such that it will minimize the choice of suspension options. Therefore, the IC socket will consist of a flexible inner socket with rigid frame using either skin fit suction suspension with a one way valve or silicon liner with locking mechanism. If a liner is used it will be sized according to manufacturer recommendations.

The NU-FlexSIV Socket will also be custom fit to each subject using standard clinical practice procedures. Subischial socket trim lines are typically 25mm distal to the ischial tuberosity and 50mm distal to the greater trochanter and while it also has a narrower medio-lateral than

Figure 5 Ischial Containment Socket (left) and NU-FlexSIV Socket (right).

PROTOCOL TITLE: Functional Performance Evaluation of the Northwestern University Flexible Sub-Ischial Vacuum (NU-FlexSIV) Socket for Persons with Transfemoral Amputation

anterior-posterior dimension, it has a more rounded cross-sectional profile than the IC socket. All subjects will be fit with an undersized liner (i.e., liner one size smaller than the manufacture recommendation based on measurements) over which the sub-ischial socket will be fitted. Using the rectification procedures specific for this design, sockets are also 4-6% undersized. Suspension will be achieved using an Össur Unity mechanical vacuum pump.

With the exception of the prosthetic foot, prosthetic components distal to the socket (the knee and pylon) will be standardized within subjects. Subjects will use their current prosthetic knee so as to minimize the burden of learning to walk with a different knee. All subjects will be provided an Össur LP Variflex foot with Unity Pump to wear with both test sockets. This foot is suitable for K3 and K4 ambulators⁵² and can interface with any existing componentry while also providing a noiseless vacuum pump for use with the sub-ischial socket condition.

The purpose of both sockets is to restore the ability to walk for someone with a transfemoral amputation. Prosthetic sockets form the interface between the residual limb and prosthesis, allowing for support of body weight and transfer of forces between the amputee and the prosthesis.

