A cross-over study has two advantages over both parallel and non-crossover longitudinal study designs. First, the influence of confounding covariates is reduced because each cross-over patient serves as their own control. This is particularly important given the custom nature of prosthetic interventions. Second, cross-over designs can be statistically efficient, requiring fewer subjects than non-cross-over designs. This is of particular benefit for prosthetic studies given the cost, time and effort involved in providing custom prosthetic devices for use every day during the study. Cross-over studies are typically subject to order effects, which in this case the most likely is shrinking of the residual limb during the first intervention phase. This shrinkage is typical of what happens any time a new, more tightly fitting socket is provided to a person with amputation. However, the effect of shrinkage is accounted for by having casting and fabrication of the second test sockets occur after data collection in the first socket is completed. While a washout period is not strictly necessary, it is effectively included as subjects will need to transition back to their usual, pre-study socket/prosthesis while the second test socket is fabricated.

Socket allocation will be concealed from the investigators until after a subject is enrolled. The starting socket design will be enclosed in sequentially numbered, opaque, sealed envelopes. Envelopes will be opened sequentially and only after the participant's name and other details are written on the appropriate envelope.

Blinding of prosthetic interventions is challenging given that they are devices that must be custom-fabricated and donned each day by the subject. Hence, for this study only the assessor, our research engineer, [name], will be blinded. To maintain blinding the assessor will remain uninformed in any aspect of the study except administration of performance and patient-reported measures and processing motion analysis data.

- The assessor will not be present for motion analysis data collection given that this requires exposure of the prosthesis and socket for appropriate marker placement. Since all that is recorded is the location of retro-reflective markers on the subject, it is not

[figure not shown]

Figure 6 Motion analysis data processing window.

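### The plan acknowledges order effects, but no socket comparison includes period: pre-specify a period term and report completers by sequence

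*Combined protocol and SAP*

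**What the plan says.** Section 11.4 acknowledges that the order in which the sockets are worn may matter, and names the likeliest cause: "which in this case the most likely is shrinking of the residual limb during the first intervention phase". It adds: "This shrinkage is typical of what happens any time a new, more tightly fitting socket is provided to a person with amputation". Two design measures follow. The first is to recast once the first socket's sessions are over: "the effect of shrinkage is accounted for by having casting and fabrication of the second test sockets occur after data collection". The second is that participants go back to their pre-study socket between periods: "While a washout period is not strictly necessary, it is effectively included". Section 3.2 also requires a residual limb of stable volume at entry.

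Section 11.1 sets out the analyses:
- Hypothesis 1: a matched pairs t-test "will be used to assess the primary outcome, Socket Comfort Score", at 6 weeks.
- Hypotheses 2a and 2b: a MANOVA "will be used to compare gait variables across socket conditions".
- Hypothesis 2c: "The difference in these timed performance tests across socket conditions will be tested using repeated measures t-tests", with a Bonferroni correction.
- Hypothesis 3 (OPUS): repeated measures t-tests, again with a Bonferroni correction.

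None of these has a period or sequence term. Section 11.1 also promises unspecified alternative approaches if assumptions look violated, and a comparison of participants with and without missing data. Nothing is to be reported by sequence. Section 23.3 gives completers only as a total: 25 needed out of 35.

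**The concern.** The trial randomises the order of the sockets, so it can separate socket from period, but the planned tests do not use that information. Two sources of a period effect are plausible.

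- **Shrinkage left after recasting.** Section 11.4 ties shrinkage to a tighter socket. Section 9.3(b) fits NU-FlexSIV with an undersized liner, and its "sockets are also 4-6% undersized"; no such undersizing is described for the IC socket. Part of any shrinkage may therefore be carryover specific to NU-FlexSIV, which a period term cannot remove. Only the part common to both sockets is at issue here.
- **Practice on the timed tests.** Section 9.2 schedules three identical sessions per socket. If week 6 is the analysis visit for these tests (section 11.1 states it only for Socket Comfort Score), it is the third session in period 1 and the sixth in period 2. That times improve with repetition is an inference. The practice trial for the Four-Square-Step Test and the best-of-three scoring of the T-Test limit it.

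With near-equal completers in the two sequences, an ignored common period effect inflates the error variance, so the test becomes conservative and loses power. With unequal completers, it also biases the socket estimate in either direction. Section 11.4 expects that some participants will struggle with the less comfortable socket. Everyone wears both sockets, though, so this does not predict which sequence loses more.

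**Working it through.** **Inputs.** From section 11.2: two-sided alpha 0.05, d = 0.754, power 0.95, N = 25. From section 23.3: 35 enrolled, 25 completers needed. Assumed: a common period effect P (period 2 minus period 1) of 0.25, 0.5 or 1 SD of the paired difference, 1 SD being an extreme; 35 participants starting 18/17, because section 9.1 gives random-size blocks but no ratio. The power figures apply to Socket Comfort Score only: the documents give no effect size for the other outcomes, and the timed-test and OPUS alphas are Bonferroni-adjusted.

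**The plan's own figure.** For a paired t-test with n = 25, the noncentrality is 0.754 × √25 = 3.77 on 24 df, giving power 0.951. With n = 24 it is 0.9425. The stated 25 reproduces.

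**Model.** Let D be NU-FlexSIV minus IC within a person, with SD 1 within each sequence. D has mean τ + P in the n1 participants who wear NU-FlexSIV second and τ − P in the n2 who wear it first.

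**Unadjusted paired t.**
- Bias = P(n1 − n2)/n. For 13:12 this is 0.04P, so at most 0.04 SD. For 15:10 at P = 0.5 it is 0.5 × 5/25 = 0.10 SD, so the estimate is 0.65 or 0.85.
- Expected variance of D = 1 + 4P²n1n2/[n(n − 1)]. For 13:12 at P = 0.5 this is 1 + 156/600 = 1.26.
- Rejection probability comes from integrating over the noncentral chi-square sum of squares (n − 1 df, noncentrality 4P²n1n2/n).

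**Period-adjusted.** The estimate is the unweighted mean of the two sequence means, with SE = ½√(1/n1 + 1/n2) and n − 2 df. For 13:12, SE = 0.2002 and noncentrality = 0.754/0.2002 = 3.77. Power does not depend on P, and type I error is 0.05.

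| Completers | P | Paired power (adverse / favourable) | Paired type I error | Adjusted power |
|---|---|---|---|---|
| 13:12 | 0 | 0.951 | 0.050 | 0.950 |
| 13:12 | 0.25 | 0.94 / 0.95 | 0.044 | 0.950 |
| 13:12 | 0.5 | 0.905 / 0.933 | 0.030 | 0.950 |
| 13:12 | 1 | 0.73 / 0.84 | 0.007 | 0.950 |
| 15:10 | 0.5 | 0.826 / 0.970 | 0.049 | 0.942 |
| 14:14 | 0.5 | 0.949 | 0.029 | 0.970 |
| 15:15 | 0.5 | 0.962 | 0.029 | 0.978 |
| 18:17 | 0.5 | 0.979 / 0.986 | 0.029 | 0.991 |

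Clear type I inflation needs 16:9 or worse: at 16:9 it is 0.07 at 0.5 SD and 0.08 at 1 SD.

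**How likely is imbalance?** With losses at random from 18/17 (hypergeometric) and 25 completers, 13:12 has a 53% chance, 15:10 or worse 15% (about 7% in a given direction), and 16:9 or worse 3%. With 28 completers, a bias of about 0.10 SD at P = 0.5 needs 17:11 or worse (4%; power 0.86 or 0.99). With 30 it needs 18:12 (2%; power 0.90 or 0.99).

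**Carryover.** Suppose carryover C = 0.5 SD reaches the second-period IC score in the NU-FlexSIV-first sequence. The adjusted estimate shifts by C/2 = 0.25 SD. The paired estimate shifts by C times that sequence's share of completers: at 13:12, 0.5 × 12/25 = 0.24 or 0.5 × 13/25 = 0.26. Adjustment does not help here.

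**The case against.** The only order effect the documents name is shrinkage, and the plan handles it by recasting, a return to the usual socket and a volume-stable entry criterion. If what remains is specific to NU-FlexSIV, a period term gains nothing. For Socket Comfort Score, no common mechanism is offered beyond leftover shrinkage; practice concerns the timed tests, for which the documents give no effect size. Serious harm also needs several assumptions at once: a 0.5 SD effect, only 25 completers, and an unlucky split in the adverse direction. Near balance the paired test is conservative, and about 28 to 30 near-equal completers offset a 0.5 SD effect.

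All of this is fair, and it limits how strongly the point can be put. It does not remove it. The design measures address shrinkage, not repeated testing. The promise of alternative approaches names no method and is not tied to period. A low chance of harm is a weak reason to omit a term that costs almost nothing.

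One caution about the remedy also stands: the contrast between sequences estimates the period effect only if there is no carryover. With carryover it mixes the two, so the reported period estimate must be read that way.

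**Conclusion.** The point holds as a recommended improvement. The plan names order effects, and none of its socket comparisons includes period. This does not make the primary test invalid. With no common period effect nothing is lost, and with near-equal completers bias is at most 0.04 SD even at the 1 SD extreme.

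At an assumed 0.5 SD and the floor of 25 completers, the paired test loses about 0.02 to 0.05 in power at 13:12. At 15:10 it is biased by 0.10 SD, with power 0.83 or 0.97. These figures rest on assumed period effects and d = 0.754; the imbalance probabilities rest on an 18/17 start with random loss. Confidence is medium, because the documents do not show how large a period effect is likely to be.

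**What to change.** In section 11.1, pre-specify period in every socket comparison:

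- **Socket Comfort Score, timed tests, OPUS:** take within-person differences (NU-FlexSIV minus IC), estimate the socket effect as the unweighted mean of the two sequence means, and use the pooled within-sequence SD with n − 2 df. A mixed model with socket, period and random participant is an alternative.
- **Gait:** run the MANOVA on within-person differences with sequence as a sum-to-zero factor. The intercept tests socket; the sequence term tests period if there is no carryover.
- **Reporting:** give the period estimate, with that condition stated, and the number of completers by sequence.
- **Limits to state:** the period term does not correct socket-specific shrinkage or informative dropout. Do not use a preliminary carryover test to choose the model.

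The cost is SAP wording and one degree of freedom; the data and N = 25 stay the same. Adjusted power at 25 completers is 0.950 (13:12), 0.942 (15:10), 0.934 (16:9) and 0.920 (17:8). Against 0.951 for the paired test with no period effect, the loss is 0.001 to 0.031.
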